1.4.3. PRIMARY OUTCOMES: Before testing the specific aims related to mediation we will test whether the intervention modifies proximal endpoints that will serve as the primary outcomes of the study. Thus, the primary endpoints will be 12-month change scores resulting from three different measurements: (1) hippocampal volume, (2) mean systolic blood pressure reactivity averaged from Stroop and Multi-Source Interference Task (MSIT) stressors during fMRI, and (3) heart rate variability. More specifically, we are predicting Time x Group interaction terms such that the exercise arm would change more than the control arm for these measures. Changes in scores of other measures including EMA-derived measures of daily life positive and negative affect, BRS, pulse wave velocity [PWV], vasodilation, CRF, resting state brain connectivity, and cortical thickness will be considered secondary and tertiary outcomes. Further, results from the structural equation modeling will be considered secondary outcomes, but will be testing the specific aims of the project.

We propose to test our primary hypotheses using a general linear mixed model (GLMM) approach because we will have three assessments for each of our measures over the course of the trial (baseline, 6-months, 12-months). The

GLMM model will include both random intercept and random slope for individual participants and a treatment-by-time interaction as a fixed effect. This technique will allow us to model the changes in the scores as a function of both time and group while also including other potentially confounding variables in the model. GLMM modeling of repeated assessments is a popular approach in clinical and longitudinal studies because it allows for random changes in measurement error and takes into account both within and between subject correlations and estimates the average growth curve across subjects and subject-specific growth curves.

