Our analysis plan has proposed an intent-to-treat analysis where all participants, regardless of whether they complete all sessions, will be invited to return for follow-up assessments. However, there will likely be some participants that refuse to return for follow-up assessments or miss a mid-point assessment. "Lost to follow up" will be defined here as missing data that is contributing to the primary outcomes. The reason will be recorded (i.e., missed visit due to traveling, illness). These criteria and documentation will also be applied for any discontinued subjects with the reasons for discontinuation being recorded (i.e., moving out of state).

Regarding the analytical approach, we propose to use all available data in the planned analysis for testing our primary outcome. Since we are examining changes over time we will be able to conduct the analysis as long as there is at

least one follow-up assessment (either at the 6-month time point or the 12-month time point). We will assess the missingness of data consistent with the assumptions of the modeling approach described above. That is, we will examine the randomness of missing data and determine if the data is missing completely at random (MCAR) or missing at random (MAR) and use maximum likelihood estimation for computation of unbiased parameters estimates and standard errors. We will not conduct multiple imputation to correct for missing data.

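### The primary endpoint is change at 12 months, but the plan does not say how time is coded in the three-visit model or which contrast decides the result

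*Combined protocol and SAP*

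**What the plan says.** Section 1.4.3 (Primary outcomes) fixes the time point: "the primary endpoints will be 12-month change scores resulting from three different measurements". The measurements are hippocampal volume, systolic blood pressure reactivity and heart rate variability. The next sentence turns this into a prediction about the model: "we are predicting Time x Group interaction terms such that the exercise arm would change more than the control arm for these measures".

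The model uses every visit, since "we will have three assessments for each of our measures over the course of the trial (baseline, 6-months, 12-months"). It is to "include both random intercept and random slope for individual participants and a treatment-by-time interaction as a fixed effect", and the section adds that such a model "estimates the average growth curve across subjects and subject-specific growth curves". Nothing states whether time enters as a number or as a visit factor, how many degrees of freedom the interaction has, or which estimate decides.

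Section 1.8.3 (Exercise compliance) says who is analysed: anyone with at "least one follow-up assessment (either at the 6-month time point or the 12-month time point"). It will "use maximum likelihood estimation for computation of unbiased parameters estimates and standard errors", without multiple imputation. Participants seen only at baseline and month 6 are therefore in the primary analysis.

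The amendment at the end of the document gives 68-83% power for hippocampal volume change, with 120 participants, 20% attrition and d of 0.5 to 0.6.

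**The concern.** An interaction over three visits can mean more than one thing. With linear time it is a difference in slopes, on 1 df. With visit as a factor the overall interaction is a joint test of the 6- and 12-month differences, on 2 df. The stated endpoint is a third quantity, the difference in change at month 12 alone. These can disagree on the same data, and the plan does not choose among them for any of its three primary endpoints. The choice could then be made after the data are seen.

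The shape of the response matters here. Sections 1.3 and 1.4.1 cite brain-volume and white-matter changes after 6 months of exercise, so an early or plateauing response is realistic. Under such a response a slope partly informed by month 6, or a joint test, answers a different question from the 12-month endpoint.

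**Working it through.** **Inputs.** From the amendment: 120 randomised (60 per arm), 20% attrition (48 per arm) and d = 0.5-0.6 for change. From section 1.4.3: visits at 0, 6 and 12 months, with random intercept and slope. No alpha is given for the primary tests, so two-sided 0.05 is assumed. Effects are in SDs of change.

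**1. The plan's own power.** Take a two-sample t-test on one change score, with noncentrality d·√(48/2) and 94 df. At d = 0.5 power is 67.9%, and at d = 0.6 it is 82.9%. The stated 68-83% is reproduced and is a one-contrast calculation.

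**2. Linear time, complete data.** With times 0, 6, 12 the least-squares slope weights are (−1, 0, +1)/12. Generalised least squares gives the same weights under each random intercept-and-slope covariance tried. Month 6 has zero weight. Twelve times the slope difference is the 12-month difference, and rejection is 5.0% when that difference is zero, whatever happens at month 6.

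**3. Linear time, a share f seen only at months 0 and 6.** The expected estimate is

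[(1−f)X′V⁻¹X + f·X₂′V₂⁻¹X₂]⁻¹ [(1−f)X′V⁻¹μ + f·X₂′V₂⁻¹μ₂],

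where subscript 2 denotes the first two visits. It reduces to d₁₂ + λ(2d₆ − d₁₂), so doubling the 6-month effect enters with weight λ. Assumptions: f = 10% or 20%, within-person correlation 0.8, random slopes making up 0-60% of the variance of 12-month change, and 60 per arm.

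| f | λ | Plateau (0.5, 0.5): estimate | Transient (0.5, 0): estimate | Transient: rejection |
|---|---|---|---|---|
| 10% | 0.026-0.048 | 0.513-0.524 | 0.026-0.048 | 5.2-5.8% |
| 20% | 0.057-0.102 | 0.528-0.551 | 0.057-0.102 | 6.0-8.2% |

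For example, at λ = 0.102 the plateau estimate is 0.5 + 0.102 × (1.0 − 0.5) = 0.551. A second set of variance assumptions gave 0.518-0.556 and 0.036-0.111. Together the ranges are about 0.51-0.56 and 0.03-0.11. With 6-month effects from 0.3 to 0.6, rejection is 5.1-6.1% at f = 10% and 5.3-9.7% at f = 20%. These figures are analytic; they were not confirmed by simulation with dropout.

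**4. Categorical time with an overall 2-df test (not in the plan).** This is a noncentral F(2, 93) with noncentrality 24·v′R⁻¹v, where v = (d₆, d₁₂) and R holds the correlation ρ of the two changes. For v = (0.5, 0) the noncentrality is 24 × 0.25/(1 − ρ²).

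| ρ | Rejection at (0.5, 0) | Power at (0.25, 0.5) |
|---|---|---|
| 0.3 | 61% | 59% |
| 0.5 | 70% | 57% |
| 0.7 | 87% | 60% |

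The single 12-month contrast gives 5% and 67.9% respectively.

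**5. Cost of the month-12 contrast.** Under the assumptions of step 3 and a linear effect (0.25, 0.5), visit as a factor gives at most 0.5 points less power than the slope. At f = 20% and 60% slope variance, for example, it is 72.9% against 73.4%.

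**The case against.** The best defence is that the plan already means the 12-month contrast. It names that time point, introduces the interaction as a more specific statement of it, and predicts a direction, which an overall 2-df test does not have. The random slope and growth-curve language point to linear time, and the power figure is for one contrast. All of this stands. It means the 2-df figures describe a test that the documents never propose.

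It also defeats a stronger reading that a reader might infer: that the slope test would itself call the trial positive with no 12-month effect. With complete data the month-6 weight is zero, so it would do so only at the nominal rate.

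The scenario in which the effect vanishes by month 12 can also be challenged. The cited 6-month findings show early response. They do not show fading while training continues, and section 1.4.1 expects larger changes in cardiovascular markers at about a year. Fading is an assumption. A plateau is plausible, but then the 12-month effect is real and only its size is slightly overstated.

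Loss at month 12 alone may also be small. The amendment reports attrition below 10% among participants not disrupted by COVID, some dropouts will miss both follow-ups, and section 1.4.2 plans pattern-mixture analyses by dropout pattern. Those are sensitivity analyses, however, and do not settle which primary estimate decides.

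**Conclusion.** The point holds as a missing specification with a modest effect under the likelier reading. The endpoint is fixed at 12 months, while the time coding and the deciding contrast are not.

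Under linear time the distortion comes mainly from participants seen at months 0 and 6 alone; uneven actual visit dates could add a little. At an assumed 10-20% of such participants, the bias is at most about 0.06 SD for a plateau and 0.11 SD for a transient effect. Rejection is about 5-8% when the 6-month effect is 0.5 and the 12-month effect is 0. The 20% case assigns all planned attrition to this one pattern, so it is towards the upper end.

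The large figures, 61-87% rejection and 57-60% power, hold only if time is categorical and the overall interaction decides. The documents do not say that this test will be used, and they do not exclude it. They do not support a claim that the trial as planned is likely to be declared positive without a 12-month effect.

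**What to change.** State in section 1.4.3 (Primary outcomes) that each primary endpoint is decided by one two-sided 1-df contrast: exercise minus control in change from baseline to month 12. Estimate it from the likelihood-based repeated-measures model with visit as a factor and unstructured covariance. Label the 6-month difference, the joint interaction test and the linear slope as supportive.

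This matches the test to the stated endpoint and to the one-contrast power calculation. It excludes the joint test as the deciding one, and it removes the linear extrapolation from month 6. Participants without a month-12 value stay in the analysis but contribute slightly less information, which costs under 1 point of power if the effect is truly linear. It takes one or two sentences and no new data.

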
sufficiently powered to test our hypotheses using structural equation modeling even after attrition. In sum, our planned sample size of 150 (N=75 per group) will be sufficient for allowing us to test our primary hypotheses.

**1.4.2. PRELIMINARY STEPS**: Prior to hypothesis testing, all data will be examined to determine: 1) frequency distributions for missing data and out-of-range values; 2) normality and internal consistency of subscales; and, 3) association between variables that may be highly correlated to guard against multicolinearity, which would inflate standard errors and make estimation

[figure not shown]

Figure 1. Diagram of exemplar full longitudinal mediational model. Paths involved in estimating longitudinal stability and residualized change are in black, paths involved in mediation are in red, and non-essential parameters are grayed out for legibility.

unstable. We will also examine the distribution of factors between groups to assess whether covariate-adjustment is required. Missing data: All outcomes will be tested using an intent-totreat (ITT) framework. Sensitivity will be explored using adherence to the intervention (e.g., per protocol). We will report reasons for dropouts and explore missing data mechanisms. To examine whether missingness is unrelated to other observed and unobserved measurements (missing completely at random, MCAR) or to the observed measurements only (missing at random, MAR), testing for completely random dropouts will be carried out. Additional sensitivity analyses test for informative dropouts. We will apply pattern-

mixture models by stratifying our data by dropout patterns and fitting separate regression models to strata.

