**1.4.3 MEDIATION:** Aim 1 has two hypotheses, (a) to test whether the peripheral effects of exercise mediate brain effects, and (b) whether the effects of exercise on the brain mediate the beneficial effects of exercise on peripheral mediators of CVD risk. We propose to test these hypotheses using longitudinal mediation models in a structural equation modeling (SEM) framework. Aim 1A: In this model, the exercise groups (X) are proposed to influence visceral control circuits (Y) via changes in peripheral pathways (M) including insulin resistance, oxidative stress, endothelial dysfunction, and CRF. We will first examine whether brain or these peripheral CVD pathways can be summarized as latent variables to control for measurement error. When using latent variables, the modeling will proceed by first establishing well-fitting measurement models, and testing for measurement invariance across waves. To test the hypothesis proposed in Aim 1A, analyses will be conducted both on a voxel-wise basis (e.g., using the BRAVO Toolbox (https://sites.google.com/site/bravotoolbox/)) or using extracted data from SPM, FSL, or FreeSurfer, depending on the imaging modality and analysis. In the latter case, we will use a theory-driven approach by selecting values from anatomical or functionally-defined regions-of-interest (ROI) on visceral control regions. Each imaging modality will be analyzed in separate models unless we have a theoretical or empirical basis for including multiple imaging metrics in a single model. We will use standard cluster-based and FDR corrections for multiple comparisons for all voxel-wise analyses and the Brain Connectivity Toolbox for graph theory metrics (i.e., segregation). Although directional hypotheses have been posited for our mediation analyses, a more conservative significance will be set at .01 to limit inflation of type 1 error. Global and incremental model fit will be verified using multiple fit-indices (chi-square, RMSEA, CFI, TLI, SRMR). With three waves of data, we will use full longitudinal mediation to test our hypotheses. Full longitudinal mediation allows us to test the effect of initial standing on the hypothesized predictor (X – Exercise group) at T1 on change in the mediator (M – peripheral CVD markers) from T1 to T2, controlling for initial standing on M, and the effect of the mediator (M– peripheral CVD measures) at T2 on the change in the outcome (Y – change in brain measure) from T2 to T3, controlling for initial value of the outcome. Mediation will be tested by calculating the indirect effect of paths that are consistent with longitudinal mediation (i.e., paths a and b in Fig. 1). Here the estimate a\*b provides a measure of the longitudinal mediated effect because it represents the effect of X at T1 on residualized change in M (path a), and M at T2

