#### 1.6 **RANDOMIZATION**:

After the completion of the baseline measures and sessions described above the participants will be randomly assigned to one of two groups. These include (a) an exercise condition that will consist of 150 minutes per week of moderate-to-vigorous intensity exercise, or (b) a PA and health information group. We will use a computer randomization protocol that will incorporate a verification that all session visits have been completed and data entered into the database. We will use a minimization algorithm with equal allocation to one of the two groups. The use of the minimization strategy will ensure treatment balance on the two factors of age at study entry (=<42, >42) and gender. Once randomized, an assigned staff member will contact the participant via phone with the group information. On this contact, the staff member will give information such as date, day, time, and location of the subject's first intervention session.

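### The primary Time x Group model does not state how baseline enters, leaves covariates to an observed-imbalance check, and does not name the minimisation factors; fixing all three in advance costs little and can only be settled before unblinding

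*Combined protocol and SAP*

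**What the plan says.** Section 1.4.3 (Primary Outcomes) states that "the primary endpoints will be 12-month change scores resulting from three different measurements": hippocampal volume, systolic blood pressure (SBP) reactivity during the fMRI stressors, and heart rate variability (HRV). The hypothesis is worded as "we are predicting Time x Group interaction terms such that the exercise arm would change more than the control arm". The model takes baseline, 6 and 12 months as its three assessments, and the "GLMM model will include both random intercept and random slope for individual participants and a treatment-by-time interaction as a fixed effect". No group main effect, constraint on the baseline means, or coding of time is given. The remark that the approach "estimates the average growth curve across subjects and subject-specific growth curves" points towards continuous time.

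On covariates, the same section speaks of modelling change "while also including other potentially confounding variables in the model" and names none. Section 1.4.2 (Preliminary Steps) adds: "We will also examine the distribution of factors between groups to assess whether covariate-adjustment is required". It gives no list and no threshold.

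Section 1.6 says that minimisation "will ensure treatment balance on the two factors of age at study entry (=<42, >42) and gender". Neither factor is named in the primary model.

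Adjustment for the starting value is written only for the mediation models, under 1.4.3 (Mediation): "controlling for initial value of the outcome".

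The Amendments section gives 68-83% power for hippocampal volume change, with 120 participants, 20% attrition and d between .5 and .6.

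**The concern.** In a randomised trial the two arms share one baseline mean in expectation. A model that uses this, or that adjusts for the baseline value, estimates the same 12-month effect with smaller variance than a comparison of change scores whenever baseline and follow-up are imperfectly correlated and have similar variances. A Time x Group model that estimates a separate baseline mean in each arm does not use it. The text does not say which of the two will be fitted, so two competent analysts could fit different primary models from it.

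The covariate rule has two weaknesses. It makes the primary model depend on what the data show. It is also unlikely to select age group and gender, because minimisation is there to keep them balanced. Factors used in the allocation belong in the analysis because they may predict change, whether or not they look unbalanced.

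The amended plan quotes 68% power at the lower end of its own effect range, so precision available from data already collected is worth having.

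**Working it through.** **1. The plan's own figure.** Inputs from the Amendments section: 120 randomised, 20% attrition, d = .5 to .6. Completers: 120 x .8 = 96, or 48 per arm. No alpha is stated for the primary tests; two-sided .05 is assumed. For a two-sample comparison the noncentrality is d x sqrt(48/2). At d=.5 this is .5 x 4.899 = 2.449. The noncentral t with 94 df gives power of 67.9% at d=.5 and 82.9% at d=.6, which reproduces 68-83%. The stated power therefore contains no gain from baseline or covariate adjustment.

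**2. Common baseline, complete data.** Let rho be the correlation between baseline and 12 months, with equal variances s² at both visits.

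- Variance of a change score: 2s²(1 - rho).
- Residual variance after baseline adjustment: s²(1 - rho²).
- Ratio: (1 - rho²) / [2(1 - rho)] = (1 + rho)/2.

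The documents give no rho, so a range is shown. d is in change-score SDs, with 48 per arm. The noncentrality is divided by the square root of the ratio; at rho=.5, for example, 2.449/sqrt(.75) = 2.828.

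| rho (assumed) | variance ratio | power, d=.5 (unadjusted 67.9%) | power, d=.6 (unadjusted 82.9%) |
|---|---|---|---|
| .5 | .750 | 79.9% | 91.9% |
| .7 | .850 | 74.8% | 88.4% |
| .9 | .950 | 70.1% | 84.7% |
| .95 | .975 | 69.0% | 83.8% |

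**3. Does partial follow-up already recover this?** Section 1.8.3 uses all available data. Take 60 per arm, 12 of them with baseline and 6 months only, categorical time, and equal correlations between visits. Generalised least squares gives these variances relative to the completer change-score contrast, for rho .5/.7/.9/.95:

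- separate baselines: .933/.941/.947/.949, power about 71/71/70/70% at d=.5;
- common baseline: .733/.821/.907/.929, power about 81/76/72/71%.

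The gain of about 10/6/2/1 points remains.

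**4. Minimisation factors.** Suppose they explain a share R² of the variance in change and are exactly balanced. If they are omitted, the standard error is too large by 1/sqrt(1 - R²), so the true type I error is about 2 x P(Z > 1.96/sqrt(1 - R²)). The exact t version gives the figures below (48 per arm, d=.5).

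| R² (assumed) | type I error, omitted | power, omitted | power, included |
|---|---|---|---|
| 5% | 4.5% | 68.3% | 70.1% |
| 10% | 3.9% | 68.8% | 72.4% |

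Inclusion adds 1.8 to 3.6 points. Main effects alone hardly alter a contrast in change; the factor-by-visit terms produce the gain.

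**5. Coding of time.** Two extreme patterns were taken: the full effect present by 6 months, and the effect appearing only after 6 months.

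- Separate baselines, linear time, complete data: the 12-month contrast is not distorted.
- Separate baselines, linear time, 12 of 60 per arm lacking month 12: about 6-8% too large under the first pattern and too small by the same amount under the second. This assumes random-intercept, slope and residual variances that the documents do not give.
- Common baseline, linear time: distorted even with complete data, by about 9% at rho=.5 and under 1% at rho=.95.
- Categorical time: no distortion from either pattern.

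**The case against.** **The text may already describe a common-baseline model.** A reader might infer that the plan gives up baseline adjustment. The documents do not establish this. Section 1.4.3 names no group main effect, and a model with time and treatment-by-time alone would constrain the arms to one baseline mean. Separate baselines are the usual fit, not the stated one. This stands, and it is a reason to write the choice down.

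**The power match proves little about the model.** This also stands. Agreement with a two-sample formula shows how power was approximated; the Amendments section itself refers to mixed effects modelling.

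**The test is valid anyway.** True. A reader might infer bias or an inflated error rate from the imbalance check. The plan does not support that: each contrast is unbiased over randomisations, and omitting balanced factors is slightly conservative. How the imbalance check itself would perform cannot be calculated, because the plan states no threshold and does not say whether the outcome's baseline value counts among the factors. Any p-value trigger would be the reader's own construction.

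**The gain may be negligible.** For hippocampal volume, the one endpoint with an explicit power figure, it is 1-2 points if the measure is very stable. For SBP reactivity and HRV it is larger only if they are less stable, which the documents do not show. It also depends on equal variances: if the 12-month SD exceeds the baseline SD by a factor 1/rho (about 5% at rho=.95), the change score is already optimal and the gain is zero. A smaller 12-month variance would raise it. These limits stand. They reduce the size of the point but give no reason to leave the model open.

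**Conclusion.** The point holds as one of precision and pre-specification, not validity. Section 1.4.3 leaves the baseline parameterisation, the covariates and the coding of time unstated, and section 1.4.2 ties covariate adjustment to observed balance.

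Under the assumptions shown, a common baseline is worth between about 1 point (rho=.95) and 12 points (rho=.5) of power at d=.5 with 48 completers per arm. The minimisation factors are worth a further 2-4 points if they explain 5-10% of the variance in change. Neither rho nor that share is in the documents, so these are ranges and not a measured loss. The change is worth making because it is nearly free and because one specification serves three primary endpoints whose stability may differ.

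**What to change.** For each of the three primary endpoints, pre-specify one model with:

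- values at 0, 6 and 12 months as responses, with visit categorical;
- one baseline mean common to both arms (with complete data, adjustment for the baseline value is essentially equivalent);
- group-by-visit terms at 6 and 12 months, with the 12-month contrast primary;
- age group (=<42, >42) and gender, each with its visit interactions, regardless of observed balance.

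State that the section 1.4.2 imbalance check does not apply to the primary model, and confine any other covariates to listed sensitivity analyses. The common baseline and categorical visits should be adopted together, since a common baseline with linear time can misstate a non-linear effect. An unstructured covariance over the three visits is a reasonable option but not essential.

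The cost is a change of wording before unblinded analysis and a few degrees of freedom. All the variables are already collected.
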